Title: Parent/Nurse Controlled Analgesia in the Neonatal Intensive Care Unit

NCT Number: NCT01823497

Document Date Feb 7, 2013 (Date of IRB approval)

Methods

This single-center, prospective, RCT was approved by the hospital Institutional Review Board, and was registered at www.clinicaltrials.gov (ID: NCT01823497) by the principal investigator prior to study enrollment.

Setting

This study took place in the NICU at Children's Hospital of Wisconsin (CHW), with data collected between April 2013 and April 2015. At the time of the study, the unit consisted of a 43 bed intensive care unit and a 16 bed step-down unit with approximately 600 admissions per year.

Procedure

Potential participants were identified from the surgery schedule and the surgical team's work list that included any infant with a planned surgery. Initially, the study team also made contact with the mothers of potential participants in the hospital's Fetal Concerns Clinic. However, this recruitment method was unsuccessful, and was therefore discontinued.

Inclusion criteria: Infants 1) born no earlier than 34 weeks post menstrual age and having a corrected age no greater than 44 weeks at the time of enrollment, 2) having a birth or current weight of at least 2 kg, 3) undergoing an abdominal or thoracic surgical procedure conducted by the pediatric general and thoracic surgery team, and 4) expected to require opioids for at least 24 hours after the surgical procedure based on the opinion of the surgeon. Additionally, at least one parent was able to read and speak English. As recruitment proved more difficult than anticipated, the protocol was amended to remove the upper age limit, but the requirement of being cared for in the NICU remained.

Exclusion criteria: Infants 1) requiring vasopressors, 2) with significant prior opioid exposure (defined as > 2 days of continual exposure before surgery, or > 3 doses over the 5 days prior to the surgery), and 3) who were expected to be chemically paralyzed after surgery.

Design

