Enrolled patients who at any point prior to PNCA or COI discontinuation, subsequently required vasopressors, a high frequency oscillating ventilator, or benzodiazepines, acetaminophen or anti-inflammatory agents as adjuncts for pain were discontinued early from the study. At the time of the study, acetaminophen was not used as routinely as it is now. In order to not confound pain assessment and opioid consumption by having some patients receive it and others not, the study team chose to stop data collection if acetaminophen (or benzodiazepine) was administered. Data collection terminated for all other patients when the PNCA or COI was discontinued. However, patient orders were monitored for 5 additional days to assess whether methadone was started.

Independent variables were collected to describe the sample and to determine whether groups were equivalent on all potentially confounding variables. Demographic and anthropometric data were extracted from the electronic health record, and included gender, race, ethnicity, gestational age, weight at time of surgery, total time PNCA or COI was used, and whether the current surgery was the infant's first. We also recorded mechanical ventilation and

any unplanned re-intubation occurrences. PNCA injections and attempts, as well as COI boluses were recorded for day (0700-1859) and nighttime (1900 – 0659) shifts. Mothers were asked about perinatal use of antidepressant or illicit drugs.

Primary Outcome

Our primary outcome was opioid consumption, defined as the average amount of opioid consumed over the time on study, and reported in mg/kg/hr. For the PNCA group, it was calculated based on the number of hourly injections plus the basal rate. For the COI group, it was based on the infusion rate across the time on study and any boluses administered.

Secondary Outcomes

- 1) Average pain intensity over the time on study. Participant pain intensity was assessed using the Revised-Face, Legs, Activity, Cry, Consolability (Revised-FLACC) scale (Malviya, Voepel-Lewis, Burke, Merkel, & Tait, 2006), the scale currently used in our NICU for this patient population. The FLACC has been used previously for NICU infants (Ahn, Kang, & Shin, 2005), has been validated in numerous pediatric populations (McGrath et al., 2008), and was originally validated in children from 2 months – 7 years (Merkel, Voepel-Lewis, Shayevitz, & Malviya, 1997).

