- 2) Adverse events, defined a priori as naloxone rescue doses and any reintubation while on the opioid delivery system. Requiring methadone after the opioid delivery system was discontinued, was used as a measure of opioid tolerance. A modified Ramsey scale was used (Hoffman et al., 2002). Nurses reported sedation scores from 1 to 6, with 1 to 3 indicating significant sedation, 4 indicating asleep and easily arouseable or awake but drowsy, 5 indicating normal awake/alert, and 6 indicating anxiety and/or pain higher than baseline. Sedation scores below 4 were considered an indication of somnolence.

3) Parent and nurse satisfaction. No satisfaction tools in the extant literature would meet study requirements, therefore the investigators developed parent (Appendix A) and nurse (Appendix B) satisfaction surveys based on our previous studies (Czarnecki et al., 2017). Parents were asked about their satisfaction with 1) the pain management for their infant and 2) their involvement in the pain management for their infant. Parents in the PNCA group were also asked how often they pushed the PNCA button. Nurses were asked about 1) their satisfaction with the method of pain management for their patient, 2) whether parents were present during their shift, 3) whether they provided education to parents, and if so, 4) how long it took to provide the education. Directions for both surveys were explained at the time of consent to parents, and to nurses during daily rounds. Additionally, the study team contacted nurses on “off shifts” by phone to remind them of the need to complete the surveys. Printed blank copies of the parent surveys were left in their infant’s NICU suite. Printed blank copies of the nurses survey were available in a 2-sided envelope in the participant’s suite, with one side used to hold blank copies, and the other side clearly labeled for completed surveys (to protect anonymity). Parents were asked to complete the survey once a day, and nurses, once each shift. The research coordinator collected completed surveys daily.

Statistical Analysis and Data Management

Data were entered into a REDCap (<http://www.project-redcap.org>) database. Bimonthly reports were generated to look for missing data, outliers, and inconsistencies. Inconsistencies were checked against original data forms and corrections made as needed. CONSORT principles (Schulz, Altman, Moher, & Group, 2011) were used to assess recruitment success.

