Statistical analyses were calculated using SPSS 24 (IBM SPSS Inc., Chicago, IL) and SAS 9.4 software (SAS Institute Inc.). An unadjusted two-sided $P < .05$ was used for statistical

significance in all analyses. Unless otherwise noted, all analyses include data from post-operative days (POD) 0-3. All participants who received the allocated intervention, and had at least one post-randomized outcome were included in the modified intent-to-treat analyses. In addition, descriptive and frequency analyses were used to provide summary information about patient characteristics. We report the median (Mdn) with Interquartile range (IQR) throughout. A Wilcoxon signed rank test was used to compare paired data of day and nighttime injections and attempts for the PNCA group, and paired day and nighttime boluses for the COI group. A Mann Whitney test was used to compare PCNA and COI groups; comparisons based on categorical data were analyzed using Chi-square or Fischer's exact tests. We used a mixed model with random post-operative day (POD) to examine the associations between opioid consumption and considered covariates, which included race, gender, surgery location, gestational age, study group and POD. Covariance structure used was AR(1), model was estimated by using maximum likelihood, POD and intercept were modelled as random effects. To meet the normality assumption of the linear mixed model, the outcome opioid consumption was transformed by using logarithm at base 10. For model selection procedure, we first included one of the considered covariates in the model to examine any time-varying effects on the outcome (univariable model analysis), then repeated the same procedure for other covariates. Based on the univariable model analyses, any covariates and interaction terms with $P < 0.20$ were included in the final multivariable analysis. The final model only includes those covariates with $P < 0.05$. Adverse events are reported based on incidence collapsed across POD.

Sample Size/Power Analysis

Based on our retrospective study (Czarnecki et al., 2014), and using an estimate of a large effect size, we planned to include 30 patients in each group (60 patients total). This sample size

would have allowed for an 80% power at 5% significance level to use a t-test to detect opioid consumption differences between groups of at least 0.74 SD. The study was terminated early however, due to difficulty recruiting, time and cost constraints.

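### As written, the POD 0-3 default leaves out naloxone and reintubation events after POD 3, although the plan defines them over all time on the delivery system

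*Combined protocol and SAP*

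**What the plan says.** Statistical Analysis and Data Management sets a general window: "Unless otherwise noted, all analyses include data from post-operative days (POD) 0-3". Its only sentence on safety is "Adverse events are reported based on incidence collapsed across POD".

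Secondary Outcomes, item 2, gives the event definition: "Adverse events, defined a priori as naloxone rescue doses and any reintubation while on the opioid delivery system". It sets no day limit. The same item describes the sedation scale and the score below which an infant counts as somnolent, again with no day limit. It then adds methadone: "Requiring methadone after the opioid delivery system was discontinued, was used as a measure of opioid tolerance".

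Protocol Details gives the collection period. For infants not withdrawn early, "Data collection terminated for all other patients when the PNCA or COI was discontinued". After that, "patient orders were monitored for 5 additional days to assess whether methadone was started".

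The inclusion criteria set a floor on expected opioid need, "expected to require opioids for at least 24 hours after the surgical procedure", but no ceiling. No section gives an expected or observed distribution of time on PNCA or COI.

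**The concern.** The outcome definition and the analysis window do not match. Naloxone and reintubation are defined over the whole period on the device and collected over that period, but the analysis default stops at POD 3 and the adverse-event sentence names no other range. Two analysts could each follow part of the text and report different event counts from the same data.

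Only infants still on the device after POD 3 can lose a naloxone or reintubation event this way, and they have the longest exposure. The trial is small (60 infants planned, stopped early), so a single uncounted event could alter the safety summary. The arms were unblinded and managed by different teams, so time on the device could differ between them. If it did, any under-count would differ too.

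**Working it through.** **The plan's own figure.** The plan states no figure for adverse events. Its one calculation is for opioid consumption, and it reproduces: a two-sided 5% t-test with 80% power and a difference of 0.74 SD needs 29.7, so 30 per group. It has no bearing on this point.

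**The texts side by side.**

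| Outcome | Period in definition or collection | Window under the default |
|---|---|---|
| Naloxone, reintubation | All time on the delivery system | POD 0-3 |
| Somnolence | No day limit given | POD 0-3 |
| Methadone | After discontinuation, five-day watch | POD 0-3 if not exempt |

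Pooling across days is compatible with either range, so the safety sentence does not state an exception.

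**Illustration of size.** The documents do not give the inputs needed to count lost events. The figures below rest on assumptions: W is the number of days in POD 0-3, D is days on the system, and daily risk is constant.

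*On-device time outside the window* = max(0, D − W) / D. With W = 4 (POD 0 counted as a full day):
- D = 4 or less: 0%
- D = 5: 1/5 = 20%
- D = 7: 3/7 = 43%
- D = 10: 6/10 = 60%

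POD 0 is normally a part-day. At the other extreme, W = 3, the shares are 1/4 = 25% at D = 4, 2/5 = 40% at D = 5, 4/7 = 57% at D = 7 and 7/10 = 70% at D = 10.

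*Whole cohort, W = 4.* Suppose a fraction f of infants stay on for D days and the rest for 3 days. The share of all on-device time lost is f(D − 4) / [fD + 3(1 − f)].
- f = 0: 0%
- f = 0.10, D = 5: 0.1/3.2 = 3%
- f = 0.25, D = 7: 0.75/4.0 = 19%
- f = 0.50, D = 7: 1.5/5.0 = 30%

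*Methadone, only if the default applied.* The share of the five-day watch falling after POD 3 = min(5, D + 5 − W) / 5. With W = 4:
- D = 1: 2/5 = 40%
- D = 2: 3/5 = 60%
- D = 3: 4/5 = 80%
- D = 4 or more: 100%

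Every infant would lose part of the watch, and anyone on the system for two days or longer would lose more than half. With W = 3, the shares are 60% at D = 1, 80% at D = 2 and 100% from D = 3.

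**The case against.** The best counter-argument is that the default yields wherever the text says otherwise, and that the outcome definitions do say otherwise. Secondary Outcomes ties naloxone and reintubation to the device period, collection runs to discontinuation, and the safety sentence can be read as pooling over all those days.

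For naloxone and reintubation this does not settle the matter. If a period named in an outcome definition counted as an exception, opioid consumption and pain would be exempt too, because both are defined over the full time on study. The default would then govern almost nothing. As drafted, it is a stated rule, and the safety sentence gives no other range.

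For methadone the argument largely stands. The plan treats it as a tolerance measure, separate from the events fixed in advance, and gives it a watch that starts only at discontinuation. A POD 3 cut would defeat that watch. A reader might infer that an infant whose device ran past POD 3 can never count as needing methadone. That follows only on the least natural reading. Even on that reading the loss would reach almost all infants, not just long users.

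It is also fair to say that nothing shows an event was lost. If no infant stayed on past POD 3, no naloxone or reintubation event is affected.

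**Conclusion.** The point holds as a conflict between the analysis window and the safety definition. Followed as written, the default excludes naloxone and reintubation events after POD 3 in infants still on PNCA or COI. For methadone, what is missing is an explicit exemption.

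The size cannot be determined. The percentages in the working depend on assumed durations, a constant daily risk and a convention for POD 0. They show how loss grows with time on the device, not how much occurred.

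A reader might go further and conclude that events were in fact removed, or that the safety comparison between arms is biased. The documents support neither. They give no durations, event counts or event times, and do not say whether time on the device differed by arm.

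**What to change.** In Statistical Analysis and Data Management, exempt safety and tolerance outcomes from the POD 0-3 default and give the window for each:

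- **Naloxone, reintubation and somnolence:** all days on the delivery system.
- **Methadone:** through five days after discontinuation.

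Report time on the device by arm, so that readers can judge exposure and see how many infants continued past POD 3. Report also, by arm, how many infants had data collection stopped early, with their events counted up to that point.

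The change should not endorse POD 0-3 for consumption or pain. Both are defined over the full time on study, so the same tension exists there and needs its own resolution.

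The cost is a few sentences and a recount of on-device data that the plan says were collected until discontinuation. There is a small downside. Follow-up time will vary between infants, so crude incidence must be read alongside exposure, and it will be incomplete for those withdrawn early. Protocol Details describes the methadone watch directly after the sentence on infants not withdrawn early, so it is unclear whether withdrawn infants were watched. The report should say.

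### A non-significant PNCA versus COI comparison, including the primary one, would be reported without an estimate or confidence interval for the group difference

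*Combined protocol and SAP*

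**What the plan says.** In the combined protocol and SAP, the Sample Size/Power Analysis section states that "we planned to include 30 patients in each group (60 patients total"), and that this number "would have allowed for an 80% power at 5% significance level" "to detect opioid consumption differences between groups of at least 0.74 SD". It closes with "The study was terminated early however, due to difficulty recruiting, time and cost constraints". The number of infants reached is not stated.

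The Statistical Analysis and Data Management section sets the reporting format: "We report the median (Mdn) with Interquartile range (IQR) throughout". For group comparisons it says "A Mann Whitney test was used to compare PCNA and COI groups", with chi-square or Fisher tests for categorical data and an unadjusted two-sided 5% threshold.

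It also describes a linear mixed model for log10 opioid consumption. Study group is one of six candidate covariates, alongside race, gender, surgery location, gestational age and post-operative day. Candidates are screened one at a time at P < 0.20, and the final model retains only those with P < 0.05.

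The document mentions no confidence interval and no effect estimate for the difference between arms.

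**The concern.** An interquartile range describes spread among infants within one arm. It does not show how precisely the difference between arms is known. A P value above 0.05 does not show that either. A reader could subtract one median from the other, but would have no measure of the uncertainty in the result.

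The mixed model is where a group estimate and standard error would normally appear. Here the randomised contrast is treated as an optional covariate. It can be dropped at the 0.20 screen or at the 0.05 retention step. The model therefore loses the treatment effect in exactly the case where an interval is most needed.

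This matters more in a trial that stopped short of its planned size. The primary outcome (opioid consumption) and the secondary outcomes (pain intensity, naloxone rescue, reintubation, methadone use, somnolence, satisfaction) could each give a non-significant result that the reported figures do not allow anyone to interpret.

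**Working it through.** **Inputs from the documents.** Planned size 30 per arm; two-sided alpha 0.05; power 80%; difference 0.74 SD; t-test (Sample Size/Power Analysis, with sidedness from Statistical Analysis). **Assumption.** The achieved number per arm is not given, so a range with equal arms is shown.

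**Step 1. Reproduce the plan's figure.** For a two-sample t-test with n per arm, the noncentrality is d × √(n/2) on 2n − 2 degrees of freedom. With d = 0.74 and n = 30 this is 0.74 × √15 = 2.87 on 58 degrees of freedom. Power is 80.5%, and the difference detectable with 80% power is 0.736 SD. The stated calculation is correct for 60 infants.

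**Step 2. What each planned comparison would show when P > 0.05.**

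| Comparison | Planned output | Estimate of group difference | Interval |
|---|---|---|---|
| Mann-Whitney | Median and IQR per arm, P | Not planned | Not planned |
| Chi-square or Fisher | Incidence per arm, P | Not planned | Not planned |
| Mixed model, log10 consumption | Covariates with P < 0.05 | Study group removed | None |

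**Step 3. How much the missing interval would tell.** The expected 95% half-width for a mean difference, in SD units, is t(0.975, 2n − 2) × √(2/n). At n = 30 this is 2.002 × √(2/30) = 0.517. P > 0.05 means that the observed difference is smaller than the half-width. The interval also excludes 0.74 SD only if the observed difference is below 0.74 minus the half-width; at n = 30 that is 0.74 − 0.517 = 0.22.

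| n per arm | Power at 0.74 SD | 80%-power difference (SD) | 95% half-width (SD) | Observed difference must be below (SD) to exclude 0.74 |
|---|---|---|---|---|
| 30 (planned) | 80.5% | 0.74 | 0.52 | 0.22 |
| 28 (assumed) | 77.6% | 0.76 | 0.54 | 0.20 |
| 25 (assumed) | 72.7% | 0.81 | 0.57 | 0.17 |
| 20 (assumed) | 62.6% | 0.91 | 0.64 | 0.10 |
| 15 (assumed) | 49.9% | 1.06 | 0.75 | none |
| 10 (assumed) | 34.7% | 1.33 | 0.94 | none |

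At 30 per arm, an observed difference of 0.10 SD gives an interval of −0.42 to 0.62, which excludes 0.74. An observed difference of 0.50 SD gives −0.02 to 1.02, which does not. Both have P > 0.05, and the planned output gives neither interval. At 15 per arm, even an observed difference of zero would not exclude 0.74 SD, because the half-width is 0.748.

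**Step 4. Rare events.** With no events in n infants, the exact two-sided 95% upper limit is 1 − 0.025^(1/n). At n = 30 it is 1 − 0.025^(1/30) = 11.6%; at an assumed n = 15 it is 1 − 0.025^(1/15) = 21.8%. A count of zero in both arms would leave rates of that size open in each.

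**The case against.** The strongest reply is that the document is candid. It says what was planned, puts the power in the conditional, and states that the trial stopped early. It does not claim 80% power for the trial as run. That stands, and the power statement is not an error.

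The achieved number is a result, and this is a methods text with no results section. Its absence here does not show that it goes unreported. That also stands. The shortfall could be trivial (28 per arm gives 77.6% power) or large, and the documents do not settle which.

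A reader might infer that the pain, adverse-event and satisfaction results are to be judged against 0.74 SD. The text ties that figure to opioid consumption only and plans no explicit conclusion of no difference, so this reading is not supported.

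Finally, the median-and-IQR sentence may only set a descriptive format, and silence on intervals does not forbid them. That is fair, but nothing commits to them. The P < 0.05 retention rule is not silence: applied as written, it removes a non-significant study-group term. This part of the point survives.

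**Conclusion.** The point holds as a gap in reporting. Followed as written, a non-significant comparison, including the primary one, would leave the reader with two medians or two incidences, a P value, and no interval for the difference. This conclusion does not depend on the achieved number: at the planned 60 the half-width is already about 0.52 SD, and it can only be wider with fewer infants at the same SD. The figures assume equal arms, a common SD and approximate normality.

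Two stronger readings should not be drawn. One is that the trial was underpowered by a known amount: the shortfall is inferred from the wording and its size is not given, so the table shows a range and not a finding. The other is that powering on a t-test and comparing by Mann-Whitney is a material fault: at 30 per arm, under normality, power moves only from 80.5% to 78.6%, which is minor.

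**What to change.** 1. Keep study group in the mixed model whatever its P value. With b the group coefficient on the log10 scale, report the PNCA/COI ratio as 10^b, with its 95% confidence limits transformed in the same way. If a study group by post-operative day term is retained, give the ratio by day.
2. For each Mann-Whitney comparison, add the Hodges-Lehmann difference with a 95% confidence interval, in mg/kg/hr for opioid consumption.
3. For adverse events, add the risk difference with an exact 95% confidence interval.
4. State that P > 0.05 will not be read as evidence of no difference, and that interpretation rests on the interval.
5. Give the numbers analysed per arm beside the 0.74 SD figure, and mark that figure as applying to the planned 60 and to opioid consumption only.

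The cost is wording and standard software output. No further enrolment or data collection is needed. The intervals may be wide, and Hodges-Lehmann intervals can be coarse where scores are heavily tied, but both would correctly describe what the data can support.
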